12.1.3. NG4 PMCF Endpoint

12.1.3.1. Hypotheses

The NG4 PMCF Primary Endpoint was designed to evaluate the safety of the NG4 device when LV MSP is enabled. In the subjects included in the NG4 PMCF Cohort, the NG4 PG-related complication free rate (CFR) at 36 months will be used to evaluate the PMCF Primary Endpoint.

A PG-related Complication will be defined as those detectable adverse events that resulted in:

- Death
- Serious injury
- Correction of PG failure requiring invasive intervention
- Permanent loss of PG device function. Permanent loss of device function is defined as any Pulse Generator (PG) that reverts to Safety Core or any PG rendered unable to deliver pacing or shocks

Complications that are determined to be associated with the PG will be considered PG-related complications (PG) and count against the PMCF endpoint. Complications related to the LV, RV, RA leads will not be counted against the PMCF endpoint.

12.1.3.2. Hypotheses

The following hypotheses will be evaluated to evaluate the safety of the NG4 device:

$$H_0: \text{PG-related CFR at 36 months} \leq 88.5\%$$

$$H_A: \text{PG-related CFR at 36 months} > 88.5\%$$

To ensure that the safety of the NG4 devices with LV MSP enabled is acceptable, the performance goal for this endpoint was based on the observed safety of prior approved Boston Scientific devices in the following studies: CAPTIVATE, LSS of 4-SITE, MADIT CRT, MultiSENSE, NAVIGATE X4. Prior devices in these studies have shown a PG-related complication-free rate of 98.5% through 36 months of follow-up. The performance goal of 88.5% was derived from the prior performance of 98.5% minus 10% to account for variability in the estimate. Expected performance of the NG4 device was based on the observed rate of prior devices.

12.1.3.3. Sample Size

A minimum of 63 subjects are required to sufficiently power the NG4 PMCF Primary Endpoint. An additional requirement is follow-up of a minimum of 60 subjects with usage of the LV MSP feature. Therefore, follow-up of 63 subjects with LV MSP enabled will satisfy both requirements. To account for the expected 15% annual attrition, a minimum of 103 subjects with LV MSP usage will be followed to achieve 63 subjects at 36 months. A minimum of the first 103 subjects identified with LV MSP usage will be included in the NG4 PMCF Cohort.

12.1.3.4. Statistical Methods

The Primary Endpoint will be calculated using Kaplan-Meier methodology. The 95% one-sided pointwise log-log confidence limit of the PG-related complication-free rate at 36 months will be compared to the performance goal of 88.5%. If the lower confidence limit exceeds 88.5%, the null hypothesis will be rejected.

12.2. *General Statistical Methods*

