12.2.2. Control of Systematic Error/Bias

Several subgroups, multivariate and other analyses are planned to evaluate the primary objective of the SMART Registry. No adjustments to the significance level (i.e., alpha) due to these multiple tests will be made. Rather, interpretation of all results will consider the biological plausibility of the findings as well as the consistency with other results obtained in this study and from other external sources.

The type I error rate for the PMCF Primary Endpoint will be contained at 5% by use of a one-sided 5% alpha in the analysis.

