12.3.5. Changes to Planned Analyses

Any changes to the planned statistical analyses made prior to performing the analyses will be documented in a Statistical Analysis Plan approved prior to performing the analyses.

Changes from the planned statistical methods after performing the analyses will be documented in the clinical study report along with a reason for the deviation.

13. Data Management

13.1. *Data Collection, Processing, and Review*

Subject data will be recorded in a limited access secure electronic data capture (EDC) system.

The clinical database will reside on a production server hosted by EDC System. All changes made to the clinical data will be captured in an electronic audit trail and available for review by the sponsor or its representative. The associated RAVE software and database have been designed to meet regulatory compliance for deployment as part of a validated system compliant with laws and regulations applicable to the conduct of clinical studies pertaining to the use of electronic records and signatures. Database backups are performed regularly.

The Investigator provides his/her electronic signature on the appropriate electronic case report forms (eCRFs) in compliance with local regulations. A written signature on printouts of the eCRFs must also be provided if required by local regulation. Changes to data previously submitted to the sponsor require a new electronic signature by the Investigator acknowledging and approving the changes.

Visual and/or electronic data review will be performed to identify possible data discrepancies. Manual and/or automatic queries will be created in the EDC system and will be issued to the site for appropriate response. Site staff will be responsible for resolving all queries in the database.

13.2. *Data Retention*

The Principal Investigator or his/her designee or participating site will maintain, at the investigative site, all essential study documents and source documentation that support the data collected on the study subjects in compliance with ICH/GCP guidelines. Documents must be retained for at least 2 years after the last approval of a marketing application or until at least 2 years have elapsed since the formal discontinuation of the registry. These documents will be retained for a longer period of time by agreement with BSC or in compliance with other country/regional/local regulations.

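### The PMCF decision rule has no answer if no PG-related complication occurs, an outcome with roughly a 29% chance at the plan's own inputs

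*Combined protocol and SAP*

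**What the plan says.** Section 12.1.3.2 tests a 36-month PG-related complication-free rate of at most 88.5% against a rate above it. The expected rate comes from earlier devices: "Prior devices in these studies have shown a PG-related complication-free rate of 98.5% through 36 months of follow-up".

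Section 12.1.3.3 asks for 63 subjects at 36 months and sets the cohort size from that: "To account for the expected 15% annual attrition, a minimum of 103 subjects with LV MSP usage will be followed".

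Section 12.1.3.4 gives the analysis. "The Primary Endpoint will be calculated using Kaplan-Meier methodology". Then: "The 95% one-sided pointwise log-log confidence limit of the PG-related complication-free rate at 36 months will be compared to the performance goal of 88.5" per cent. The decision follows: "If the lower confidence limit exceeds 88.5%, the null hypothesis will be rejected".

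Section 12.2.2 sets the error rate: "The type I error rate for the PMCF Primary Endpoint will be contained at 5% by use of a one-sided 5% alpha".

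No section says which limit applies, or what is concluded, if no PG-related complication is seen. Section 12.3.5 says that changes made before the analysis "will be documented in a Statistical Analysis Plan approved prior to performing the analyses", but it supplies no zero-event rule.

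**The concern.** The named limit exists only if there is at least one event. With none, there is nothing to compare with 88.5%, and the rule neither rejects nor retains the null hypothesis. An endpoint expected to run at 98.5% in about 100 subjects will often produce no events, so this is a likely outcome.

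This is the only endpoint in the study with a stated null and alternative, and the cohort exists to support the CE mark. If zero events occur, someone must choose a limit after seeing the data, or accept what the software prints. A blank limit does not exceed 88.5%, whereas a limit set to 100% does. Under section 12.3.5, a change of method made after the analysis has to be reported as a deviation with a reason. That would be an avoidable blemish on a favourable result.

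**Working it through.** **Inputs from the plan.** Expected rate 98.5% and goal 88.5% (12.1.3.2); at least 103 subjects, 15% annual attrition, 63 at 36 months (12.1.3.3); one-sided 95% log-log Kaplan-Meier limit (12.1.3.4).

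**Assumptions.** The event hazard is constant and attrition is steady at 15% a year. The documents do not give event timing.

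**The plan's own figure.** 63 / 0.85^3 = 102.6, rounded up to 103; and 103 × 0.85^3 = 63.3. The 103 is reproduced.

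**Why the limit fails at zero events.** The lower limit is S^exp(z × SE), where SE = √V / |log S|, V is the Greenwood sum and z = 1.645.

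- One event among 63 complete subjects: S = 62/63 = 0.984, √V = √(1/(63 × 62)) = 0.0160, |log S| = 0.0160, so SE = 1.00. The limit is 0.984^exp(1.645) = 92.0%.
- No event: S = 1, V = 0, log S = 0, so SE = 0/0. The point estimate is still 100%; only the limit is missing.

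**Chance of zero events at 98.5%.**

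- Event hazard h = −ln(0.985)/3 = 0.00504 per year; attrition hazard m = −ln(0.85) = 0.1625 per year.
- Chance that a subject has an observed event by 36 months: h/(h+m) × (1 − exp(−3(h+m))) = 0.0301 × (1 − 0.985 × 0.614) = 0.0119.
- Expected events: 103 × 0.0119 = 1.22. Chance of none: (1 − 0.0119)^103 = 29.2%.

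| Case | P(0 events) |
|---|---|
| 103 subjects with attrition | 29% |
| All 103 complete: 0.985^103 | 21% |
| Only 63 count: 0.985^63 | 39% |
| 130 subjects with attrition | 21% |
| 150 subjects with attrition | 17% |
| 200 subjects with attrition | 9% |

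**How the rule behaves by event count.** Simulation of the Kaplan-Meier log-log rule: 103 subjects with attrition, true rate 98.5%, 40,000 runs.

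| Events | Share of runs | Limit above 88.5% |
|---|---|---|
| 0 | 29.1% | no limit |
| 1 | 36.1% | 100% |
| 2 | 22.1% | 100% |
| 3 | 9.1% | 98% |
| 4 | 2.8% | 75% |

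The limit is defined and above 88.5% in 69.4% of all runs. Adding the zero-event runs as passes gives 69.4% + 29.1% = 98.5%.

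**The exact limit at zero events.** With no event in n subjects, the exact one-sided 95% lower limit is 0.05^(1/n). It is 95.4% at n = 63. It crosses 88.5% between n = 24 (88.3%) and n = 25 (88.7%). In the simulation, the number at risk at 36 months had a median of 62, a 95% range of 52 to 72 and a minimum of 41. The corresponding limits are 94.4% (n = 52), 95.9% (n = 72) and 93.0% (n = 41), all well clear of the goal.

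**Type I error.** At a true rate of 88.5%, the simulated rejection rate is about 3.6% with or without the zero-event rule, because zero events then has a probability of only about 0.005%.

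**The case against.** The strongest reply is that the conclusion is not really in doubt. The rule already passes with one event, and every usual zero-event bound clears the goal at n = 63: exact 95.4%, 1 − 3/n = 95.2%, Wilson 63/(63 + 1.645²) = 95.9%. A choice made after the fact does harm mainly when reasonable choices disagree, and here they agree. That stands, and it limits the severity. It does not supply the missing rule, and a literal or software-driven reading can still return no decision.

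Second, the 69% treats a complication-free cohort as not meeting the goal, which no section says. That is right. It is a worst-case reading and should not be quoted as the power of the design.

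Third, the 29% depends on its assumptions. Events concentrated early would move it towards 21%, and 103 is a minimum. Both points stand, which is why the range is given. Even 9% at 200 subjects is common enough to need a rule.

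Fourth, section 12.3.5 lets a SAP settle such detail. It does, but that is a place for the rule and not the rule itself.

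Finally, counting only those at risk at 36 months drops subjects censored earlier, although section 12.2.1 has the whole cohort contributing. It can also order results oddly: one event with 103 at risk gives a log-log limit of 95.1%, while zero events with n = 52 gives 94.4%. This is true and conservative, and it does not alter pass or fail.

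**Conclusion.** The concern holds. The decision rule for the PMCF endpoint is undefined at zero events, and no section provides a fallback. At the plan's inputs, with a constant hazard and steady attrition, the chance of this is about 29%. It is 21% to 39% between the two extremes of follow-up for 103 subjects, and lower if the cohort grows (9% at 200). Type I error is not affected. If an undefined limit were scored as not rejecting, the chance of success at 98.5% would be 69% instead of 98.5%; that scoring is an assumption and not something the plan says. The gap does not threaten the validity of the study. It should be closed before the analysis, because the outcome is likely and the remedy is nearly free.

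**What to change.** Before the analysis, add to section 12.1.3.4, or to the SAP under section 12.3.5:

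> If no PG-related complication occurs by 36 months, the one-sided 95% lower confidence limit will be the exact limit 0.05^(1/n), where n is the number of subjects at risk at 36 months.

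Keep the log-log limit whenever at least one event occurs. State the day that defines 36 months, since the visit window runs from day 1050 to day 1110 after enrollment; the existing Kaplan-Meier limit needs that day too.

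The cost is one sentence and a few lines of code, with no more patients or visits. The zero-event limit is slightly conservative because earlier-censored subjects are left out of n.

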12.2.1. Analysis Sets

All subjects with complete Clinical Composite Score data at 12 months will contribute to the analyses evaluating CRT Response rates. All subjects in the NG4 PMCF Cohort will contribute data to the PMCF Primary Endpoint.

12.2.2. Control of Systematic Error/Bias

Several subgroups, multivariate and other analyses are planned to evaluate the primary objective of the SMART Registry. No adjustments to the significance level (i.e., alpha) due to these multiple tests will be made. Rather, interpretation of all results will consider the biological plausibility of the findings as well as the consistency with other results obtained in this study and from other external sources.

The type I error rate for the PMCF Primary Endpoint will be contained at 5% by use of a one-sided 5% alpha in the analysis.

12.2.3. Number of Subjects per Investigative Site

Sites will be allowed to enroll a maximum of 200 subjects, equal to 10% of the SMART Registry expected enrollment.

12.3. *Data Analyses*

12.3.1. Other Endpoints/Measurements

Additional analyses may be performed to assist in the evaluation of the Primary Objective:

- CRT Response in the overall cohort and in subgroups using groupings of the three levels of the Clinical Composite Score:
 - Improved vs. Unchanged/Worsened
 - Improved/Unchanged vs. Worsened
- Evaluation of the components of the Clinical Composite Score in the overall cohort and in subgroups:
 - All-cause mortality
 - Heart failure events
 - NYHA Class
 - Quality of life (patient Global Assessment instrument)

Utilization patterns of device features and diagnostics will also be calculated, if available:

- MultiSite Pacing (MSP)
 - Number and percent of subjects with MSP usage overall and throughout follow-up
 - Physician rationale for utilizing MSP
 - Programming parameters (i.e., vectors) associated with MSP usage
- HeartLogic use (if available)
 - Number and percent of subjects with HeartLogic usage overall and throughout follow-up
 - Physician rationale for utilizing HeartLogic
 - Physician response to HeartLogic alerts
- SmartDelay
 - Number and percent of subjects with SmartDelay usage
- Vector Guide
 - Number and percent of subjects with Vector Guide usage
- Programming of pacing vectors
 - Rationale for selection of pacing vector (e.g., lowest pacing capture threshold without extracardiac stimulation, longest RV-LV delay, etc.)

12.3.2. Interim Analyses

No formal interim analyses are planned for stopping for superiority or futility. Interim analyses may be performed to support publications. Analysis of each endpoint will be performed when all applicable data for that endpoint has been collected.

12.3.3. Subgroup Analyses

The list of baseline covariates (with applicable subgroups in parentheses) includes, but is not necessarily limited to:

- Ischemic Etiology (Ischemic vs Non-Ischemic)
- Bundle Branch Block morphology (LBBB vs Non-LBBB)
- NYHA class (I/II vs III/IV)
- Presence of atrial fibrillation (Yes or No)
- Diabetes (Yes vs. No)
- Sex (Male vs. Female)
- Age < 65 years vs. ≥ 65 years
- RV-LV electrical delay (< 70 ms vs. ≥ 70 ms)
- QRS-LV at the implantation site
- QRS width (< 150 ms vs. ≥ 150 ms)

CRT Response rates (Full Registry) and PG-related complication-free rates (NG PMCF Cohort) will be compared between the two subgroups for each covariate. A Cochran-Armitage test for trend will be performed to compare CRT Response rates across subgroups. A log-rank test will be used to compare PG-related complication-free rates across subgroups. Additional cutpoints may be evaluated for continuous covariates, based on the data and/or clinical determination.

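### The PMCF subgroup log-rank tests would rest on about one event, so their usual p-values are unreliable in small subgroups and uninformative in balanced ones

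*Combined protocol and SAP*

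**What the plan says.** Section 12.3.3 lists ten baseline covariates, nine of them with two stated levels. The list is left open, and further cutpoints for continuous covariates may be chosen from the data. The section then prescribes one test for each endpoint. CRT Response in the full registry gets a Cochran-Armitage test. For the PMCF cohort the text is: "A log-rank test will be used to compare PG-related complication-free rates across subgroups". It gives no significance level, reference distribution, minimum number of events or rule for sparse data.

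The planning figures for the same endpoint are in Sections 12.1.3.1 to 12.1.3.3:

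- **Event rate:** "Prior devices in these studies have shown a PG-related complication-free rate of 98.5% through 36 months of follow-up", and "Expected performance of the NG4 device was based on the observed rate of prior devices".
- **Cohort size and attrition:** "To account for the expected 15% annual attrition, a minimum of 103 subjects with LV MSP usage will be followed". The 103 are meant to leave 63 subjects at 36 months.
- **Events that count:** "Complications related to the LV, RV, RA leads will not be counted against the PMCF endpoint".

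Section 12.2.2 sets a one-sided 5% level, but for the PMCF primary endpoint only.

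**The concern.** A cohort of about 100 with an expected 1.5% event rate will have almost no events to divide between subgroups. The chi-square approximation behind the ordinary log-rank p-value needs more than one or two events. With one event, the statistic depends almost entirely on how large the affected subgroup is and says little about device safety.

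Two misreadings are at stake in a safety report meant to support CE Mark. A single chance complication in a small subgroup could be reported as a significant difference. Non-significance in evenly split subgroups could be taken as reassurance when the test had almost no ability to reject.

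**Working it through.** **Inputs.** 98.5% complication-free at 36 months (12.1.3.2); a minimum of 103 subjects, 63 remaining at 36 months, and 15% annual attrition (12.1.3.3). Assumptions: constant hazards, analysis to 36 months, and a two-sided 5% log-rank test with chi-square reference.

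**Step 1: the plan's own figure.** 63 / 0.85³ = 63 / 0.6141 = 102.6, rounded up to 103. This reproduces.

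**Step 2: expected events.**
- Event hazard λ = −ln(0.985)/3 = 0.00504 per year.
- Attrition hazard μ = −ln(0.85) = 0.1625 per year.
- Expected events = 103 × λ/(λ+μ) × [1 − exp(−3(λ+μ))] = 103 × 0.0301 × 0.395 = 1.22.
- Simple bounds: 63 × 1.5% = 0.95 and 103 × 1.5% = 1.55.
- Poisson with mean 1.22: no event 29%, one 36%, two 22%, three 9%, four or more 3.6%.

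With no event the log-rank statistic is undefined.

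**Step 3: one event.** If it falls in a subgroup holding share q of those at risk, observed minus expected is 1 − q and the variance is q(1 − q). The chi-square is therefore (1 − q)/q. It exceeds 3.84 when q < 1/(1 + 3.84) = 0.207, about 21 of 103 subjects. With no true difference, the event falls in that subgroup with probability q. For a share below one half, q is also the exact two-sided p-value.

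| Share q | Chi-square | Nominal p | Exact probability | Rejection given exactly one event | Unconditional rejection |
|---|---|---|---|---|---|
| 5% | 19.0 | 0.00001 | 0.05 | 4.9% | 5.2% |
| 10% | 9.0 | 0.003 | 0.10 | 9.6% | 5.7% |
| 15% | 5.67 | 0.017 | 0.15 | 14.9% | 6.5% |
| 20% | 4.0 | 0.046 | 0.20 | 10.9% | 5.6% |
| 25% | 3.0 | 0.083 | 0.25 | 0.5% | 1.9% |
| 50% | 1.0 | 0.317 | 0.50 | 0% | 0.27% |

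The last two columns are simulated with no true difference (103 subjects, 36 months, 100,000 runs per share). A second simulation of 20,000 runs per share gave unconditional rates of 5.8%, 6.4% and 5.7% at 10%, 15% and 20%. Rejection given one event is lower at 20% than at 15% because 21 of 103 is 20.4%, close to the threshold, and attrition often moves the share above it.

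**Step 4: balanced split.** If all k events fall on one side, chi-square is about k. Three events give p = 0.083 and four give 0.046, so at least four are needed, all in one half. With a fivefold hazard in one half, the simulated rejection rate is only 18%. For 80% power at a hazard ratio of 3, the events needed are 27 in a balanced split or 41 at a 20% share.

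**Step 5: sensitivity** (illustrative assumptions, not plan figures).

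| Case | Expected events | Balanced rejection, no difference |
|---|---|---|
| 103 subjects, five-year follow-up | 1.8 | 0.8% |
| 200 subjects, 36 months | 2.4 | 1.7% |
| 103 subjects, true rate 88.5% | 9.4 | about 5% |

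**The case against.** - **The long-run error rate is close to nominal.** This stands. A reader might infer from the one-event p-values that the tests reject far too often overall. They do not: the rate is about 5.5 to 6.5% at shares of 10 to 20%, and well below 5% from a 25% share upward. What fails is the p-value as reported once an event has occurred, for example 0.003 where the exact value is 0.10.
- **Failure to reject in a balanced split is low power, not invalidity.** Also correct. Section 12.1.3.3 powers only the primary PMCF endpoint, and the plan claims no power for subgroups. The balanced case shows that a null result is uninformative; it does not show an inflated error.
- **The plan does not say the test is two-sided, at 5% or asymptotic.** True. These are assumptions, and the wording does not exclude an exact version. Nor does it call for one, and the ordinary version is the natural reading.
- **No affected covariate can be named.** True. The documents give no subgroup shares, so they do not support a claim that any particular covariate will produce a false signal.
- **103 is a minimum, and follow-up continues past 36 months until the last cohort subject reaches that visit (Section 11.8).** True, but Step 5 shows that events remain sparse with longer follow-up or a larger cohort.
- **The analyses are exploratory, and Section 12.2.2 says interpretation will weigh biological plausibility and consistency.** This is partial mitigation. That paragraph opens with the registry's primary objective, and cautious reading does not correct a wrong p-value.

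**Conclusion.** The point holds in a limited form. At the plan's own figures the PMCF subgroup log-rank tests would have about 1.2 events. Under the assumed two-sided 5% chi-square reference, a single event in a subgroup below about 20.7% of the risk set gives a nominal p several times or more too small (0.046, 0.017 and 0.003 at shares of 20%, 15% and 10%, against 0.20, 0.15 and 0.10). In evenly split subgroups a non-significant result carries almost no information.

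This depends on the 98.5% planning rate and a cohort near the stated minimum. If the true rate were near 88.5%, the ordinary test would have a size of about 4 to 5%.

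A reader might go further and infer that the PMCF safety conclusion is compromised. The documents do not support that. The primary decision compares a single-cohort Kaplan-Meier lower limit with 88.5% at a one-sided 5% level (12.1.3.4 and 12.2.2), and no decision rule depends on the subgroup tests.

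**What to change.** In Section 12.3.3, keep the significance tests for CRT Response. For the PMCF cohort, replace the log-rank sentence with a descriptive listing of PG-related complications by covariate, giving for each subgroup the event count, the denominator and an exact confidence interval. If a p-value is wanted, specify an exact (permutation) log-rank test and label it exploratory. It needs no minimum event count for validity, although it assumes similar censoring in the two subgroups.

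The cost is one sentence, and Section 12.3.5 already allows such a change through a SAP approved before the analysis. The sponsor gives up conventional p-values that carry little information at the planned event rate. An exact test will rarely reach significance: a balanced split would need six events, all on one side (2 × 0.5⁶ = 0.031). That fairly reflects how little the data can say.
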